#### 6.1.14.5. Columbia Suicidal-Severity Rating Scale

Suicide-related thoughts and behaviors, based on the Columbia-Suicide Severity Rating Scale (C-SSRS), will be summarized by treatment group for Study Period II, Study Period III, and Study Period IV. In particular, for each of the following suicide-related events, the number and percent of patients with the event will be enumerated by treatment group: completed suicide, nonfatal suicide attempt, interrupted attempt, aborted attempt, preparatory acts or behavior, active suicidal ideation with specific plan and intent, active suicidal ideation with some intent to act without specific plan, active suicidal ideation with any methods (no plan) without intent to act, nonspecific active suicidal thoughts, and wish to be dead. In addition, the number and percent of patients who experienced at least one of various composite measures will be presented. These include suicidal behavior (completed suicide, non-fatal suicidal attempts, interrupted attempts, aborted attempts, and preparatory acts or behavior), suicidal act (completed suicide, non-fatal suicidal attempts), suicidal ideation [active suicidal ideation with specific plan and intent, active suicidal ideation with some intent to act without specific plan, active suicidal

ideation with any methods (no plan) without intent to act, non-specific active suicidal thoughts, and wish to be dead]. Table HMGW.6.9 is a shell of the format that will be followed for Study Period II. Similar tables but without treatment comparison will be created for Study Period III and Study Period IV.

Specifically, the following outcomes are C-SSRS categories and have binary responses (yes/no). The categories have been re-ordered from the actual scale in an increasing order of severity from 1 to 10 to facilitate the definitions of the comparative endpoints.

- Category 1 – Wish to be Dead
- Category 2 – Non-specific Active Suicidal Thoughts
- Category 3 – Active Suicidal Ideation with Any Methods (Not Plan) without Intent to Act
- Category 4 – Active Suicidal Ideation with Some Intent to Act, without Specific Plan
- Category 5 – Active Suicidal Ideation with Specific Plan and Intent
- Category 6 – Preparatory Acts or Behavior
- Category 7 – Aborted Attempt
- Category 8 – Interrupted Attempt
- Category 9 – Actual Attempt (non-fatal)
- Category 10 – Completed Suicide

The following outcomes are numerical scores derived from the C-SSRS categories. The scores are created at each assessment for each patient.

- **Suicidal Ideation Score:** The maximum suicidal ideation category (1-5 on the C-SSRS) present at the assessment. Assign a score of 0 if no ideation is present.
- **Suicidal Behavior Score:** The maximum suicidal behavior category (6-10 on the C-SSRS) present at the assessment. Assign a score of 0 if no behavior is present.
- **Suicidal Act Score:** The maximum suicidal act category (9-10 on the C-SSRS) present at the assessment. Assign a score of 0 if no act is present.
- **Suicidal Ideation or Behavior Score:** The maximum suicidal ideation or behavior category (1-10 on the C-SSRS) present at the assessment. Assign a score of 0 if no ideation or behavior is present.

Composite endpoints based on the above categories are defined below.

- **Suicidal ideation:** A “yes” answer at any time during treatment to any one of the five suicidal ideation questions (Categories 1-5) on the C-SSRS.
- **Suicidal behavior:** A “yes” answer at any time during treatment to any one of the five suicidal behavior questions (Categories 6-10) on the C-SSRS.
- **Suicidal act:** A “yes” answer at any time during treatment to any one of the two suicidal act questions (Categories 9-10) on the C-SSRS.
- **Suicidal ideation or behavior:** A “yes” answer at any time during treatment to any one of the ten suicidal ideation and behavior questions (Categories 1-10) on the C-SSRS.

In addition, non-suicidal self-injurious behavior will be summarized and compared between treatment groups as shown in Table HMGW.6.9.

Also, the number and percent of patients with at least one of the following composite measures will be presented by treatment group for Study Period II and Study Period III separately: treatment-emergent suicidal ideation, treatment-emergent suicidal behavior, emergence of serious suicidal ideation, improvement in suicidal ideation at endpoint, treatment-emergent suicidal behavior or ideation, and treatment-emergent non-suicidal self-injurious behavior. Taper emergent suicide-related events in suicidal ideation or behavior, and taper emergent non-suicidal self-injurious behavior during taper phase will also be summarized. Table HMGW.6.10 is a shell of the format that will be followed. Treatment-emergent events will be assessed in 2 ways: compared to lifetime baseline and compared to lead-in baseline. The definitions of lifetime and lead-in baseline for Study Period II are as following and also described in Table HMGW.6.1. For details of baseline definitions for Study Period III and study Period IV, see table HMGW.6.1.

**Lifetime Baseline** = suicide information collected on the Columbia-Suicide Severity Rating Scale (C-SSRS) Baseline form plus information collected on the C-SSRS “Since Last Visit” form during any lead-in period prior to randomization. Lifetime baseline is used to capture all the prior history.

**Lead-in Baseline** = information collected on the C-SSRS “Since Last Visit” form at all visits prior to randomization. Lead-in baseline is used to capture only recent history

Treatment emergent/taper emergent suicidal ideation (category 1-5) compared to lifetime (or lead-in) baseline is defined as an increase in maximum suicidal ideation over lifetime (or lead-in) baseline during the study period, or any ideation during the study period, if there was none at lifetime (or lead-in) baseline. Treatment emergent/taper emergent suicidal behavior (category 6-10) compared to lifetime (or lead-in) baseline is defined as an increase in maximum suicidal behavior over lifetime (or lead-in) baseline during the study period, or any behavior during the study period, if there was none at lifetime (or lead-in) baseline. Emergence of serious suicidal ideation compared to lifetime (or lead-in) baseline is defined as an increase in the maximum suicidal ideation score to 4 or 5 during study period from no suicidal ideation (scores of 0) at lifetime (or lead-in) baseline. Improvement in suicidal ideation at endpoint compared to baseline is defined as a decrease in suicidal ideation score at endpoint (the last nonmissing measurement during study period) from the lead-in baseline. Treatment-emergent suicidal ideation or behavior compared to lifetime (lead-in) baseline is defined as an increase in maximum suicidal ideation or behavior over lifetime (or lead-in) baseline during the study period, or any ideation or behavior during the study period, if there was none at lifetime (or lead-in) baseline.

If the number of patients with post-baseline suicide-related events is greater than or equal to 4, then shift tables will be also be used to summarize the data. Table HMGW.6.11 and Table HMGW.6.12 are shells of format that show the number and percentage of patients with shifts between the most severe event category at baseline and the most severe event category post-baseline by treatment group, for Study Period II and lifetime baseline. Similar tables will be created for Study Period II and lead-in baseline, and Study Period III with both baselines if needed.

Subjects who discontinued from the study with no post-baseline C-SSRS value will be considered unevaluable for analyses of suicidality. Only evaluable subjects will be considered in the analyses.

Fisher's exact test will be used for treatment comparison for Study Period II. For each event, p-values will only be displayed if at least 4 events occurred in at least one treatment group.

A listing of patients with suicidal ideation or behavior will be displayed. For patients with suicidal ideation or behavior at any time, data from all visits are displayed. See the listing HMGW.6.13.

**Table HMGW.6.9 Number of Patients with Suicide-Related Events Based on the C-SSRS During Treatment; All Randomized Patients**

Events during treatment	Duloxetine N=xx n (%)	Placebo N=xx n (%)	p-values a (to compare percentages)
Suicidal Ideation (1-5)	x (%)	x (%)	0.xxx
1 – Wish to be dead	x (%)	x (%)	
2 – Non-specific active suicidal thoughts	x (%)	x (%)	
3 – Active suicidal ideation with any methods (not plan) without intent to act	x (%)	x (%)	
4 – Active suicidal ideation with some intent to act, without specific plan	x (%)	x (%)	
5 – Active suicidal ideation with specific plan and intent	x (%)	x (%)	
Suicidal Behavior (6-10)	x (%)	x (%)	0.xxx
6 – Preparatory acts or behavior	x (%)	x (%)	
7 – Aborted attempt	x (%)	x (%)	
8 – Interrupted attempt	x (%)	x (%)	
Suicidal Act (9-10)			
9 – Non-fatal suicide attempt	x (%)	x (%)	
10 – Completed suicide	x (%)	x (%)	
Suicidal Ideation or Behavior (1-10)	x (%)	x (%)	0.xxx

Non-suicidal Self-injurious	x (%)	x (%)	0.xxx
-----------------------------	-------	-------	-------

a p-values are from Fisher's exact test.

Notes: N = number of enrolled patients with at least one post-baseline C-SSRS assessment. In this table, n and (%) refer to the number and percent of patients who experience the event at least once during treatment. For the composite endpoint of suicidal ideation (1-5), n and (%) refer to the number and percent of patients who experience any one of the five suicidal ideation events at least once during treatment. For the composite endpoint of suicidal behavior (6-10), n and (%) refer to the number and percent of patients who experience any one of the five suicidal behavior events at least once during treatment. For the composite endpoint of suicidal ideation or behavior (1-10), n and (%) refer to the number and percent of patients who experience any one of the ten suicidal ideation or behavior events at least once during treatment.

**Table HMGW.6.10 Number of Patients with Suicide-Related Treatment-Emergent Events Based on the C-SSRS During Treatment; All Randomized Patients**

Treatment-emergent (TE) Events	Duloxetine		Placebo		p-values a
	N	n (%)	N	n (%)	
TE Suicidal ideation (1-5) compared to lifetime baseline b	xx	x (%)	xx	x (%)	0.xxx
TE Suicidal ideation (1-5) compared to lead-in baseline b	xx	x (%)	xx	x (%)	0.xxx
Emergence of serious suicidal ideation (4-5) compared to lifetime baseline c	xx	x (%)	xx	x (%)	0.xxx
Emergence of serious suicidal ideation (4-5) compared to lead-in baseline c	xx	x (%)	xx	x (%)	0.xxx
Improvement in suicidal ideation at endpoint compared with lead-in baseline d	xx	x (%)	xx	x (%)	0.xxx
TE Suicidal behavior (6-10) compared to lifetime baseline e	xx	x (%)	xx	x (%)	0.xxx
TE Suicidal behavior (6-10) compared to lead-in baseline e	xx	x (%)	xx	x (%)	0.xxx
TE Suicidal ideation or behavior compared to lifetime baseline f	xx	x (%)	xx	x (%)	0.xxx

TE Suicidal ideation or behavior compared to lead-in baseline f	xx	x (%)	xx	x (%)	0.xxx
TE Non-suicidal self-injurious compared to lifetime baseline e	xx	x (%)	xx	x (%)	0.xxx
TE Non-suicidal self-injurious compared to lead-in baseline e	xx	x (%)	xx	x (%)	0.xxx

a p-values are from Fisher's exact test.

b N=Number of randomized patients with at least one post-baseline suicidal ideation score and whose maximum C-SSRS suicidal ideation score during the comparison period is non-missing and <5.

c N=Number of randomized patients with at least one post-baseline suicidal ideation score and whose maximum C-SSRS suicidal ideation score during the comparison period is 0.

d N=Number of randomized patients with at least one post-baseline suicidal ideation score and whose suicidal ideation score is non-missing and >0 just prior to treatment.

e N=Number of randomized patients with baseline and at least one post-baseline C-SSRS suicidal behavior score.

f N=Number of randomized patients with baseline and at least one post-baseline C-SSRS suicidal ideation or behavior score.

g N=number of randomized patients without non-suicidal self-injurious behavior at baseline and with at least one post-baseline non-suicidal self-injurious behavior score.

Notes: For the composite endpoint of suicidal ideation (1-5), n and (%) refer to the number and percent of patients who experience treatment-emergent suicidal ideation during treatment. For the composite endpoint of suicidal behavior (6-10), n and (%) refer to the number and percent of patients who experience treatment-emergent suicidal behavior during treatment.

**Table HMGW.6.11 Shift-table to Demonstrate Changes in C-SSRS Categories from Baseline During Treatment; All Randomized Patients**

Treatment	Maximum Baseline Category	Maximum During Treatment		
		No suicidal ideation or behavior n (%)	Suicidal ideation n (%)	Suicidal behavior n (%)
Duloxetine (N=xxx)	No suicidal ideation or behavior	x (%)	x (%)	x (%)
	Suicidal Ideation	x (%)	x (%)	x (%)
	Suicidal Behavior	x (%)	x (%)	x (%)
Placebo (N=xxx)	No suicidal ideation or behavior	x (%)	x (%)	x (%)

	Suicidal Ideation	x (%)	x (%)	x (%)
	Suicidal Behavior	x (%)	x (%)	x (%)

Notes: N = number of patients with a baseline and post-baseline C-SSRS assessment, n = number of patients in category. % = 100\*n/N.

Baseline refers to the screening period; Maximum refers to the category associated with the maximum C-SSRS suicidal ideation or behavior score during treatment (0 = least severe, 10 = most severe) where 0=No Suicidal Ideation or Behavior, 1=Wish to be Dead, 2=Non-specific Active Suicidal Thoughts, 3=Active Suicidal Ideation with Any Methods (Not Plan) without Intent to Act, 4=Active Suicidal Ideation with Some Intent to Act, without Specific Plan, 5=Active Suicidal Ideation with Specific Plan and Intent, 6=Preparatory Acts or Behavior, 7=Aborted Attempt, 8= Interrupted Attempt, 9=Actual Attempt (non-fatal), 10=Completed Suicide.

**Table HMGW.6.12 Shift-table to Demonstrate Changes in C-SSRS Suicidal Ideation Scores from Baseline During Treatment; All Randomized Patients**

Treatment	Maximum Baseline Score	Maximum Suicidal Ideation Score During Treatment					
		0 n (%)	1 n (%)	2 n (%)	3 n (%)	4 n (%)	5 n (%)
Duloxetine (N=xxx)	0	x (%)	x (%)	x (%)	x (%)	x (%)	x (%)
	1	x (%)	x (%)	x (%)	x (%)	x (%)	x (%)
	2	x (%)	x (%)	x (%)	x (%)	x (%)	x (%)
	3	x (%)	x (%)	x (%)	x (%)	x (%)	x (%)
	4	x (%)	x (%)	x (%)	x (%)	x (%)	x (%)
	5	x (%)	x (%)	x (%)	x (%)	x (%)	x (%)
Placebo (N=xxx)	0	x (%)	x (%)	x (%)	x (%)	x (%)	x (%)
	1	x (%)	x (%)	x (%)	x (%)	x (%)	x (%)
	2	x (%)	x (%)	x (%)	x (%)	x (%)	x (%)
	3	x (%)	x (%)	x (%)	x (%)	x (%)	x (%)
	4	x (%)	x (%)	x (%)	x (%)	x (%)	x (%)
	5	x (%)	x (%)	x (%)	x (%)	x (%)	x (%)

Notes: N = number of patients with a baseline and post-baseline C-SSRS suicidal ideation score, n = number of patients in category, % = 100\*n/N.

Baseline refers to screening period; Maximum refers to the maximum C-SSRS suicidal ideation score during treatment (0 = least severe, 5 = most severe) where 0=No Suicidal Ideation, 1=Wish to be Dead, 2=Non-specific Active Suicidal Thoughts, 3=Active

Suicidal Ideation with Any Methods (Not Plan) without Intent to Act, 4=Active Suicidal Ideation with Some Intent to Act, without Specific Plan, and 5=Active Suicidal Ideation with Specific Plan and Intent.

**Listing HMGW.6.13 Listing of C-SSRS Suicidal Ideation and Behavior Dataa and Non-suicidal Self-injurious Data; All Randomized Patients; Study Period II ,III and IV.**

Investigator ID	Patient ID	Treatment	Visit	Suicidal Ideation					Suicidal Behavior					Non-suicidal Self-injurious
				1	2	3	4	5	6	7	8	9	10	
	XXXX			Yes	Yes	Yes	No	Yes	No	No	No	No	No	

Note: Only patients with suicidal ideation or behavior are displayed. For patients with suicidal ideation or behavior at any time, data from all visits are displayed.

a Key: 1=Wish to be Dead, 2=Non-specific Active Suicidal Thoughts, 3=Active Suicidal Ideation with Any Methods (Not Plan) without Intent to Act, 4=Active Suicidal Ideation with Some Intent to Act, without Specific Plan, 5=Active Suicidal Ideation with Specific Plan and Intent, 6=Preparatory Acts or Behavior, 7=Aborted Attempt, 8= Interrupted Attempt, 9=Actual Attempt (non-fatal), 10=Completed Suicide.

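### Listing HMGW.6.13 is titled to include non-suicidal self-injury, but its selection rule leaves out patients with self-injury alone; a probable footnote slip affects the same outcome in Table HMGW.6.10

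*SAP*

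**What the plan says.** All of this is in SAP Section 6.1.14.5.

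- **Outcome.** After defining the ideation and behavior composites, the text adds that "non-suicidal self-injurious behavior will be summarized and compared between treatment groups as shown in Table HMGW.6.9". It also plans treatment-emergent and taper-emergent self-injury summaries.
- **Suicidal behavior.** The composite is a yes to "any one of the five suicidal behavior questions (Categories 6-10) on the C-SSRS". Ideation is categories 1-5. Self-injury without suicidal intent is not one of the ten categories.
- **Listing HMGW.6.13.** The title covers "Non-suicidal Self-injurious Data; All Randomized Patients; Study Period II ,III and IV", and the last column is for self-injury. The note under the shell reads "Note: Only patients with suicidal ideation or behavior are displayed". The body text agrees with the note: "A listing of patients with suicidal ideation or behavior will be displayed".
- **Table HMGW.6.10.** The row "TE Non-suicidal self-injurious compared to lifetime baseline" and its lead-in counterpart both carry footnote e. That footnote counts randomized patients who have a suicidal behavior score at baseline and at least once afterwards. Footnote g reads "N=number of randomized patients without non-suicidal self-injurious behavior at baseline and with at least one post-baseline non-suicidal self-injurious behavior score". No row cites it.

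The Revision History (Section 3) records that self-injury analyses were added to this section after version 1.

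**The concern.** The listing cannot deliver what its title announces. Its self-injury column can be filled only for patients who also had suicidal ideation or behavior. Patients whose only event is self-injury contribute to the counts, but the C-SSRS listing shows neither the visit, nor the treatment at the time, nor the pattern across visits. In an adolescent trial that compares this outcome between arms, a safety reader would want to trace those cases from the table to the patient.

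The footnote question concerns the denominator of the treatment-emergent rows. Footnote e refers to a different C-SSRS item and keeps patients who already had self-injury at baseline. If emergence means a new yes on a yes/no item, those patients cannot become cases, so keeping them lowers the reported proportion. The body text does not settle the matter: it defines emergence for ideation and for behavior, but not for self-injury.

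**Working it through.** **Listing.** No arithmetic applies, so I followed each type of patient through the rules.

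| C-SSRS finding at any time | Counted for self-injury in Table HMGW.6.9 | Shown in Listing HMGW.6.13 |
|---|---|---|
| Ideation or behavior (categories 1-10), no self-injury | No | Yes |
| Ideation or behavior, and self-injury | Yes | Yes |
| Self-injury only | Yes, if during treatment | No |

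The third row is the gap. The note and the body text give the same rule, so neither repairs the other. Only the title and the column point the other way.

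**Footnote.** The SAP states no figure to reproduce, so what follows is an illustration.

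Inputs:
- About 184 patients randomized 1:1 (Section 5.2), so 184/2 = 92 per arm. All are taken as evaluable, which is an assumption.
- Proportion p with self-injury at baseline: 5% to 30%, an assumption.
- Emergent cases: 8 in one arm and 2 in the other, an assumption.

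Under footnote e the denominator is 92. Under footnote g it is 92 minus the number with baseline self-injury, about 92 × (1 − p). The e-proportion divided by the g-proportion is therefore about 1 − p.

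| p | Denominator under g | 8 cases under e | 8 cases under g | Ratio e/g |
|---|---|---|---|---|
| 5% | 87 | 8/92 = 8.7% | 8/87 = 9.2% | 0.95 |
| 10% | 83 | 8.7% | 8/83 = 9.6% | 0.90 |
| 20% | 74 | 8.7% | 8/74 = 10.8% | 0.80 |
| 30% | 64 | 8.7% | 8/64 = 12.5% | 0.70 |

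Fisher's exact test, two-sided, 8 versus 2 cases:

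| Excluded at baseline (8-case arm, 2-case arm) | p-value |
|---|---|
| none (footnote e) | 0.100 |
| 9, 9 | 0.099 |
| 18, 18 | 0.097 |
| 18, 9 | 0.047 |
| 9, 18 | 0.104 |

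With equal exclusions the ratio of proportions stays at 4.0 (for example 8/74 over 2/74), and the p-value hardly changes. It moves materially in only one of the two imbalanced cases.

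The table applies more naturally to the lifetime row. Table HMGW.6.1 places the Study Period II lead-in baseline at Visit 2, and the text describes lead-in as recent history only. Prevalence on that row is then likely lower, and the effect nearer the top of the table.

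**The case against.** **Listing.** The note and the body text agree, and the title can be read as naming the columns shown for the patients selected. No sentence promises to list patients with self-injury alone. That reading is possible, but it leaves a compared outcome with no C-SSRS listing of its own cases, under a title that refers to all randomized patients. The inconsistency stands.

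A reader might infer that these patients are never listed anywhere, or that their treatment arm is hidden. The SAP does not support that. Tables HMGW.6.9 and HMGW.6.10 count self-injury by arm, and Section 6.1.14.1 plans listings of adverse events, serious events and discontinuations due to adverse events. A self-injury event reported as an adverse event would appear there. The SAP does not say whether every such event is reported that way, so the gap is confined to Listing HMGW.6.13 but is not shown to be filled elsewhere.

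**Footnote.** Footnote g names this outcome, and the two self-injury rows are the only ones it fits. A superscript g may have been mistyped, or misread when the text was taken from the PDF. A programmer would probably see that a suicidal behavior score does not fit a non-suicidal outcome. This objection largely succeeds: the intended denominator is already written under the table, so the point is an editorial correction.

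A reader might also infer that the between-arm comparison is distorted. The calculation shows little effect without marked baseline imbalance, and the SAP gives no baseline rates from which to expect one. Moreover, p-values are displayed only when at least one arm has four or more events.

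**Conclusion.** The listing point holds as a matter of text and rests on no assumption: as written, the selection rule omits every patient with self-injury alone from the only C-SSRS listing. How many that is cannot be said, because the SAP gives no rate.

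The footnote point holds on the text at hand but is probably a letter slip. Taken literally, it would lower the treatment-emergent proportion by a factor of about 1 − p, that is 0.95 to 0.70 for an assumed baseline prevalence of 5% to 30%, and likely by less on the lead-in row. It assumes that emergence means a new yes in a patient without one at baseline, which the SAP does not state for this outcome.

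Overall severity is low. Both points concern safety displays; the primary analysis, its error rate and the futility rule are not affected.

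**What to change.** 1. In the body-text sentence introducing the listing and in the note under Listing HMGW.6.13, change the rule to: patients with suicidal ideation, suicidal behavior or non-suicidal self-injurious behavior at any time. Extend the companion sentence about showing all visits in the same way.
2. In Table HMGW.6.10, attach footnote g to both treatment-emergent self-injury rows, with baseline meaning lifetime or lead-in as the row states.
3. Preferably, add one sentence to the body text defining treatment-emergent self-injury against each baseline, next to the existing definitions for ideation and behavior.

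The cost is a few words and two footnote letters, plus a one-line change to the listing program's selection. The tables already use the self-injury item, so no new data are needed.
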